2. **Cardiovascular disease (CVD) event:** Typically includes MI (heart attack), PTCA (angioplasty/stenting), bypass surgery, stroke, peripheral vascular disease (arterial blockages in arms or legs leading to procedure or surgery). Less common CVD problems would be new cardiac arrhythmias (e.g., new atrial fibrillation) or new valvular disease (e.g., mitral or aortic regurgitation).
3. **DVT/PE (deep vein thrombosis/pulmonary embolism, i.e., blood clots in the venous system):**
4. **Participant choice:** Participants may choose to remove themselves from the study by informing the research team in writing or verbally at any point during the study.

The following will be monitored and can lead to the participant being withdrawn at any point by the PI:

1. **Expired breath carbon monoxide increase:** If the average of two consecutive CO measurements in the same visit is
 - i. CO is greater than 50 ppm if CO at baseline visit 1 is <20 ppm.
 - ii. CO is greater than 60 ppm if CO at baseline visit is 1 20 – 34 ppm.
 - iii. CO is greater than 70 ppm if CO at baseline visit is 1 35 – 49 ppm.
 - iv. CO is greater than 80 ppm if CO at baseline visit is 1 50 – 60 ppm.
 - v. CO is greater than 90 ppm if CO at baseline visit is 1 61 – 70 ppm.If the average of the two readings is still out of range after testing twice, an AE will be documented and the participant will be monitored by the medical professional.
2. **Cigarette per day increase:** The average CPD increases by more than 100% from the average CPD at the baseline assessment visit.
3. **Increase Systolic Blood Pressure** over >160 mmHg
4. **Increased substance abuse** in which the participant is behaving inappropriately at visits or demonstrates an inability to continue with the study.
5. **Any hospitalization or debilitation** in which participation in the study could be detrimental to the recovery process. This will be self-reported by the participant and will be reviewed by the site PI and medical professional to determine whether continued participation in the study is appropriate.
6. **Any Missed visits** where the participant would have received new research cigarettes. Of concern is what type of cigarettes (research or own brand) the participant has been smoking if they did not attend a visit where they would have received research cigarettes. Participants will be reviewed and considered for withdrawal on a case by case basis.

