3.3.2. Follow-up for withdrawn subjects

Subjects are withdrawn if they provide a verbal or written request to be removed from the study at any time after the initial consent. All data collected up to the withdrawal date will be included in the analysis of the data with Intent to Treat statistical rules. If a subject consents but is not randomized, or is consented but does not complete the baseline evaluation and assessments, the subject will be replaced. Subjects who withdraw themselves will be asked to complete a questionnaire (named End of Trial Questionnaire in Appendix of Coordinator entered Surveys) regarding the reasons for dropping out. Subjects that were selected to use a topography machine (see below) will be asked to use the machine for 1 additional day.

4. Recruitment Methods

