4.2. Recruitment process

This will be a randomized trial of cigarette smokers (n=400 with an expected dropout rate of 30% for a total of 280 smokers) recruited at two sites: Pennsylvania State University (n=200) and George Washington University (n=200). Recruitment materials will direct cigarette smokers to contact the study center by telephone or visit the Penn State TCORS website to complete the basic eligibility screener also called the Call routing screener- IRB protocol STUDY00002213). Once they complete this screener and they are eligible for one of our studies, they will be forwarded to the appropriate study coordinator for further screening.

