To determine the modifying effect of menthol on progressive nicotine content reduction and biomarkers: modification effects such as the menthol will be examined by incorporating the menthol-by-group interaction in the multi-variable linear mixed model. The three-way interaction of the menthol-by-group-by-time will be explored but will be removed from the model if not significant. If the menthol-by-group interaction were found significant then mean-profile plot will be used to show the interaction in details.

To determine the predictors of participant drop-out/relapse: it is hypothesized that compensatory smoking behavior as measured by smoking topography and expired carbon monoxide, a higher baseline nicotine dependence behavioral score and rapid nicotine metabolism phenotypes will be associated with drop-out/relapse. The status of drop-out/relapse will be combined with the length of time from randomization to drop-out/relapse or loss of follow-up to form a time-to-event type of variable. Participants who completed the randomization phase of study will be considered as censored records. Kaplan-Meier type analysis (for categorical predictors) or simple Cox proportional hazard regression model (for quantitative predictors) will be used to examine the bivariate associations between the possible predictors and time to drop-out. If a predictor has shown marginal significance (with p-value less than 0.10) in the bivariate analysis then it will be kept in the multiple regression analysis. A multi-variable Cox proportional hazard regression

model will be built to examine the effects of the predictors jointly for time to drop-out. The magnitude and direction of effectiveness will be quantified by the estimated hazard ratios with their 95% confidence intervals. The interaction between the predictors will be explored in the analysis but will be removed if not significant.

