15.2. Compensation for research-related injury

It is the policy of the institution to provide neither financial compensation nor free medical treatment for research-related injury. In the event of injury resulting from this research, medical treatment is available but will be provided at the usual charge. Costs for the treatment of research-related injuries will be charged to subjects or their insurance carriers.

16. Number of Subjects

The project will recruit a total of 400 participants. We will recruit 200 participants at Penn State Hershey, allowing for a 30% withdraw rate and 280 subjects needed to complete the entire protocol.

17. Resources Available

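### Letting topography, requested from only 100 people, into the joint Aim 2 Cox model can cut it from at most about 120 events to at most about 30; separately, the coding of withdrawals for raised CO is not stated

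*Combined protocol and SAP*

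**What the plan says.** All references are to the combined protocol and SAP.

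- **Outcome (Section 9.2, predictors of drop-out/relapse).** Status is combined with the "length of time from randomization to drop-out/relapse or loss of follow-up". On censoring, the text says "Participants who completed the randomization phase of study will be considered as censored records". No other group is named as censored. Neither drop-out nor relapse is defined, and withdrawal by the PI is not mentioned.
- **Predictors (Section 9.2).** The hypothesis names "compensatory smoking behavior as measured by smoking topography and expired carbon monoxide", a higher baseline dependence score and rapid nicotine metabolism.
- **Selection (Section 9.2).** The rule begins "If a predictor has shown marginal significance (with p-value less than 0.10") in the bivariate step; such a predictor stays for the multiple regression. One multivariable Cox model then examines the predictors jointly. No method for missing covariates is given.
- **Topography.** Section 7.2.1 requests it from a random subset of 100, chosen at Visit 1. Section 1.3.3 lists four measures: puff volume, count, duration and intensity.
- **Withdrawal by the PI (Section 3.3.1).** The list opens "The following will be monitored and can lead to the participant being withdrawn at any point by the PI". Item 1 is raised CO, item 2 is cigarettes per day up by more than 100%, and item 9 requires both and applies only to those receiving research cigarettes.
- **Attrition.** Section 4.2 has "n=400 with an expected dropout rate of 30% for a total of 280 smokers"; Section 16 has "allowing for a 30% withdraw rate and 280 subjects needed to complete the entire protocol". Section 3.3.2 gives people who withdraw themselves a questionnaire "regarding the reasons for dropping out".

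**The concern.** The joint model is where Aim 2 estimates each predictor's effect given the others. Its sample is decided by a screening p-value. If no topography measure passes, the model can use everyone randomised. If one passes, a default fit drops everyone without topography, and the other predictors lose about three quarters of their events even though they are not confined to the topography subset. Nothing in Section 9.2 prevents this.

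The second question is what counts as an event. Raised CO can lead to withdrawal by the PI, and expired CO is a hypothesised predictor of drop-out. If those withdrawals are events, part of any CO association could come from the withdrawal rule and not from participants' own decisions to leave. Section 9.2 also does not say whether CO enters as the baseline value, a value from the preceding visit, or the value at the visit of withdrawal.

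**Working it through.** **Plan's own figure.** 280 / (1 − 0.30) = 400, so the recruitment target reproduces. The documents give no event count or power for Aim 2.

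**Events.** Full sample: 400 × 0.30 = 120. Topography subset: 100 × 0.30 = 30. If 100 means per site, which the text does not say: 200 × 0.30 = 60. These are upper-end figures for two reasons:

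- Section 16 ties the 30% to the entire protocol (33 weeks, Section 7.3), while the Cox model covers the 18-week randomised phase.
- The 100 are chosen before randomisation. An assumed 10% to 30% loss before randomisation would leave 27 to 21 events (100 × 0.90 × 0.30; 100 × 0.70 × 0.30).

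**Precision.** For a predictor scaled to SD 1 and uncorrelated with the others, at two-sided 0.05 with d events:

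- detectable HR at 80% power = exp((1.960 + 0.842)/√d)
- power for HR 1.30 = Φ(√d × ln 1.30 − 1.960), with ln 1.30 = 0.2624

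| Events | Detectable HR per SD | Power for HR 1.30 |
|---|---|---|
| 120 | 1.29 | 82% |
| 60 | 1.44 | 53% |
| 30 | 1.67 | 30% |

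**How easily topography enters.** With four null measures, each tested at 0.10, the chance that at least one passes is 1 − 0.9⁴ = 34% if they are independent. It is 29% at an assumed pairwise correlation of 0.5 and 21% at 0.8. If the hypothesis about topography is right, entry is more likely.

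**Coding of withdrawals.** Sections 4.2 and 16 give the same loss from 400 to 280 as a drop-out rate and as a withdrawal rate, which is an all-cause use. Section 3.3.2 applies dropping out to people who leave by their own choice. CO withdrawals are events on the first use and not on the second.

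**Size of the CO effect.** Let K be the number of CO withdrawals, which the documents do not give. In simulations of 400 participants with 30% voluntary drop-out unrelated to CO and assumed CO distributions, counting K = 2 as events gave a 6–7% false-positive rate for baseline CO against a nominal 5%. At K = 6 the rate ran from 7–10% (preceding-visit CO, visit variation independent) to 34–52% (the triggering reading itself as covariate). Coded as change from baseline it was 4–8% if any lasting CO elevation was already present in the baseline reading, and higher if the rise began after it. With these withdrawals censored it was 4–6%, which follows from the set-up. The spread shows that the answer depends on K and on the CO coding; none of these rates is an estimate for this trial.

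**The case against.** **On topography.** A complete-case fit is the software default, not something the plan states, and the loss arises only if a topography measure passes screening. A reader might infer that the results would be biased. The documents do not support that: the subset is randomly selected, so the loss is of precision. Nor does a separate subset model rescue topography, which still has about 30 events or fewer; it protects the other predictors. All of this stands, but the plan leaves the sample for its joint model to a screening result and a default.

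**On CO.** A reader might infer that Aim 2 is circular, or that a null CO effect would be declared several times too often. The documents do not support either:

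- The circularity needs the all-cause reading, and Section 3.3 distinguishes withdrawal by the PI from participants who withdraw themselves.
- K may be near zero. Item 1 of the PI list ends in an adverse event record and monitoring, withdrawal is discretionary, and Section 12 calls earlier compensation minimal. Item 9 needs cigarettes per day above 200% of baseline, while the supply is 150% of baseline (Section 7.2), so study cigarettes alone would rarely meet it.
- The hypothesis concerns compensation, which is a rise, and Sections 11.2 and 11.7 express CO as an increase from baseline. The largest simulated rates come from using the triggering reading as the covariate, which the plan does not propose.

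These points stand. What remains is that the coding is unstated and is cheap to settle before analysis.

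**Conclusion.** The topography point holds. If one measure enters and the fit uses complete cases, the joint model goes from at most about 120 events to at most about 30. The detectable HR per SD moves from 1.29 to 1.67, and power for HR 1.30 from 82% to 30%, for every predictor in the model. If the subset is 100 per site, the figures are 60 events, 1.44 and 53%. This rests on the planned 30% attrition and on complete-case fitting.

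The CO point holds only conditionally. It requires that PI withdrawals count as events and that some occur for raised CO. Its size cannot be stated from the documents.

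Both points concern the Aim 2 predictor model and not the comparison between arms. They should be corrected in the SAP.

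**What to change.** 1. **Topography.** Fit the main multivariable Cox model in all randomised participants without topography, whatever its bivariate p-value. Report topography in a separate subset model, labelled as having about 30 events or fewer. The cost is that the main model is not adjusted for topography.
2. **Withdrawals.** Define drop-out and relapse, and state how loss to follow-up is coded. In the Cox model used to judge CO, treat CO and cigarettes-per-day withdrawals as competing events, censored at withdrawal. Report the all-cause model as a sensitivity analysis, with counts by reason. No rule that both models must agree is needed. Censoring strong compensators may be informative, which is why the all-cause model is shown, and the competing-event model has slightly fewer events.
3. **CO timing.** Enter CO as change from baseline at the last visit before the risk interval, never the reading that triggered withdrawal. Name the baseline visit: if it is the randomisation visit, the change is zero for everyone in the first three-week interval. This coding does not replace step 2.
4. **Reconciliation.** In Section 3.3.1, items 1 and 2 of the PI list (CO or cigarettes per day alone) and item 9 (both, only if receiving research cigarettes) do not agree. The sponsor must reconcile them, because they decide which non-completers left because of CO.

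The cost is SAP wording and one REDCap field for withdrawal reason and date. CO is already measured at every clinic visit (Section 11.4), and the adverse event log already records action taken (Section 11.3).

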1.1. Study Objectives

Specific Aims

1. Determine the effect of progressive nicotine content reduction on nicotine and its metabolites and other biomarkers of smoking exposure.
 - a. Determine the effects of RNC (reduced nicotine content) cigarettes in both black and white smokers of lower SES (socioeconomic status) over an 18 week trial period. Subjects will be randomized to either, (i) gradual reduction in reduced nicotine content cigarettes, or (ii) cigarettes containing the nicotine content of their usual brand. It is expected that the gradual reduction of nicotine from progressively lowering nicotine exposure will lead to lower levels of blood nicotine metabolites and nicotine-derived 4-(methylnitrosamino)-1-(3-pyridyl)-1-butanol)(NNAL), while not affecting cigarettes smoked per.
 - b. Determine the modifying effect of menthol on progressive nicotine content reduction and biomarkers. It is expected that menthol will not modify the effect of progressive RNC cigarettes on the above biomarkers.
2. Determine the predictors of participant drop-out/relapse. We hypothesize that compensatory smoking behavior as measured by smoking topography and expired carbon monoxide (CO), a higher baseline nicotine dependence behavioral score, will be associated with dropout/ relapse.
3. Determine if a gradual reduction in RNC cigarettes vs. same nicotine content is associated with a reduction in stress. Psychological stress and nicotine stimulate the production of cortisol, a biomarker of stress pathways. It is expected that nicotine reduction will lead to initially higher levels

of psychological stress and cortisol associated with withdrawal but lowered levels of psychological stress/cortisol with long-term nicotine reduction.

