The FSPTCA is based on the premise that making tobacco less or non-addictive will result in a reduction in harm from tobacco smoke [27, 28]. This premise would apply for all aspects of nicotine dependence including smoking onset in non-addicted youths and smoking cessation in current dependent smokers. Although it is well known that compensatory smoking behavior (e.g. more frequent puffs or inhaling deeper) limits the ability to reduce nicotine exposure, at least in commercially available higher nicotine cigarettes [29], the feasibility of progressively switching to low nicotine cigarettes was considered to be technically feasible by the American Medical Association and other authoritative groups [28, 30]. A broad-based policy needs to consider the diverse population of smokers who vary substantially by socio-demographic, economic and cultural factors that may affect nicotine dependence and the choice of tobacco products smoked. In an initial report by Benowitz et al. [4] of a randomized trial of a specially blended low nicotine cigarette with features similar to Marlboro brand cigarettes, 130 smokers progressively lowered their nicotine over a 6-month period. There was a concurrent decrease in exposure to nicotine or nicotine derived carcinogen biomarkers such as cotinine and NNAL. In this trial, the mean level of education in participants was college graduation (e.g. ~15-16 years of education) and nearly all subjects were white. A similar trial by Hatsukami et al. [2] of 165 smokers that used commercially available Quest cigarettes assigned to two different low nicotine cigarettes for 6 weeks had similar findings.

A potential policy measure of lowered nicotine exposure through reduced nicotine yield cigarettes needs to specifically address whether lowered nicotine tobacco products reduces nicotine exposure given that smokers undertake compensatory smoking behaviors to maintain constant nicotine intake. The policy also requires that reduced nicotine cigarettes not increase exposure to tobacco smoke toxins and carcinogens, as well as decrease the levels of physiological dependence and smoking behaviors associated with nicotine dependence. This needs to be documented prior to the full endorsement of the policy [28] and will be the major focus of this proposal.

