7.1. Study Design

This will be a two-arm randomized double-blinded trial. The study will proceed in four phases.

1. In Baseline Phase 1, subjects will smoke their own usual brand of cigarettes for 1 week to get acclimated to study participation.
2. In Baseline Phase 2, participants will be assigned (unblinded) to use research cigarettes that contain the normal amount of nicotine of conventional store bought cigarettes and matched on the participants' menthol flavor preference (menthol or non-menthol) for 2 weeks. Participants who complete this 2 week period of smoking research cigarettes and agree to continue with the study will enter the Randomized Double-Blind Phase.
3. During Randomization Phase 3, participants will be randomized to either:
 - a. continue to smoke the same research cigarettes for a further 18 weeks
 - b. switch to progressively reduced nicotine content (RNC) cigarettes over the next 18 weeks
4. Finally, during Treatment Choice Phase 4, both groups will then be offered the choice to:
 - a. return to their usual brand
 - b. Receive assistance to quit smoking (with counseling and FDA-approved medication provided at no cost for 11 weeks)

Table 1: Dosing Schedule for smokers enrolled in the study prior to 12/19/16

Phase:	Baseline I	Baseline II	Randomized Double-Blind Phase					Treatment Choice Phase**
Wks/Phase:	1	2	3	3	3	3	6	12
Cigarette type:	Own Brand	Usual Nicotine Research Cigarettes	Reduced Nicotine Step 1	Reduced Nicotine Step 2	Reduced Nicotine Step 3	Reduced Nicotine Step 4	Reduced Nicotine Step 5	Variable
Nicotine content (mg/cigarette)[†]								
regular: RNC	Around 11mg	11.0	7.8	3.2	1.3	0.7	0.2	Variable
		12.1	7.0	3.4	1.4	0.7	0.2	
regular: UNC	Around 11mg	11.0	11.0	11.0	11.0	11.0	11.0	Variable*
		12.1	12.1	12.1	12.1	12.1	12.1	

*Menthol smokers randomized to the UNC treatment group who choose to stay on study cigarettes will switch to a 9.9 mg or 12.1 mg cigarette type determined by the time of entry into the study due to a 12.1 mg menthol study cigarette supply shortage. A consent form addendum will be filled out for all menthol smokers who choose to stay on study cigarettes in the Treatment Choice Phase.

Table 2: Dosing Schedule for smokers enrolled 12/19/16 or after

Phase:	Baseline I	Baseline II	Randomized Double-Blind Phase					Treatment Choice Phase**
Wks/Phase:	1	2	3	3	3	3	6	12

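### Aim 2 drop-out models do not require treatment arm or say when compensation is measured, so arm differences can pass as an effect of compensatory smoking

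*Combined protocol and SAP*

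**What the plan says.** Aim 2 (Section 1.1) hypothesises that compensatory smoking, measured by topography and expired CO, is associated with drop-out or relapse, as is higher baseline dependence. Section 9.2 adds rapid nicotine metabolism.

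The outcome in 9.2 is the "length of time from randomization to drop-out/relapse or loss of follow-up", with those who complete the randomised phase censored. The analysis has two steps:

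- **Screen.** Kaplan-Meier is used for categorical predictors. For the others, a "simple Cox proportional hazard regression model (for quantitative predictors) will be used to examine the bivariate associations between the possible predictors" and time to drop-out. Predictors are kept if they show marginal significance ("with p-value less than 0.10").
- **Joint model.** A multivariable Cox "model will be built to examine the effects of the predictors jointly for time to drop-out". On interactions: "The interaction between the predictors will be explored in the analysis but will be removed if not significant".

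Arm is not named in either step as predictor, covariate, stratum or interaction. The mixed models for Aims 1 and 3, in the same section, name both group and time-by-group. The rule on known confounders in 9.2 is written for the linear models only.

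Of the Aim 2 predictors, only dependence is labelled as a baseline value. No visit, change score or time-varying rule is given for CO or topography.

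**The concern.** Section 2.3 presents compensation as a response to lower nicotine: "smokers undertake compensatory smoking behaviors to maintain constant nicotine intake". After randomisation the reduced-nicotine arm steps down five times (Section 7.1, Tables 1 and 2), while the control arm is to "continue to smoke the same research cigarettes for a further 18 weeks". The response to the randomised cut can therefore be seen only after randomisation, in one arm.

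This leaves two readings of the plan. If CO or puffing is taken before randomisation, it cannot measure the response to the cut. If it is taken afterwards, arm may shift both the predictor and the risk of drop-out, and a model without arm credits some of the arm effect to the predictor. The direction cannot be known in advance. The earlier study summarised in Section 2.2 saw CO fall with 0.05 mg yield cigarettes and rise with 0.3 mg yield cigarettes. A spurious result could support the hypothesis or contradict it. Product compliance/drop-out is the only primary endpoint listed in Section 1.2, and these are the only models for drop-out in 9.2.

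**Working it through.** **Plan figures.** Section 9.1 gives 280 completers and 30% drop-out: 280 / (1 − 0.30) = 400, which reproduces. Expected drop-outs are 400 × 0.30 = 120. Allocation is 1:1 (Section 7.4.3). There is no event count or power statement for Aim 2, so there is no Aim 2 figure to reproduce.

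**Assumptions.** The documents give neither the split of drop-out by arm nor the shift in CO or puffing. I hold overall drop-out at 30% and vary the split (control/reduced nicotine). The predictor has SD 1 within arm, its mean differs by δ between arms, and it has no effect on drop-out within either arm.

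**Arm hazard ratio**, constant hazard over 18 weeks: HR = ln(1 − p₁) / ln(1 − p₀).
- 25%/35%: ln 0.65 / ln 0.75 = 1.497, so β = ln HR = 0.404.
- 20%/40%: ln 0.60 / ln 0.80 = 2.289, so β = 0.828.

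**Spurious signal when arm is left out**, approximately: λ = (δβ/4) × √120 / √(1 + δ²/4). The chance of p < 0.05 is Φ(λ − 1.96) + Φ(−λ − 1.96). For example, at 20%/40% and δ = 0.5, λ = 0.1035 × 10.95 / 1.031 = 1.10, giving 0.195 + 0.001 = 19.6%.

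| Drop-out | δ | Formula, no arm term | Simulation, no arm term | Simulation, arm term |
|---|---|---|---|---|
| 30%/30% | 0.25–0.8 | 5% | 5–6% | 5–6% |
| 25%/35% | 0.25 | 5.9% | 5.8% | 5.1% |
| 25%/35% | 0.5 | 8.4% | 8.9% | 5.9% |
| 25%/35% | 0.8 | 13.0% | 14.6% | 5.1% |
| 20%/40% | 0.25 | 8.7% | 9.8% | 5.6% |
| 20%/40% | 0.5 | 19.6% | 18.5% | 5.1% |
| 20%/40% | 0.8 | 39% | 37.7% | 5.7% |

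The simulations fit Cox models to 400 participants, 2,000 trials per row. Separate simulations gave ranges of 5–12% and 9–35% over the same shifts, so the upper ends are best read as 12–15% and 35–39%. The spurious hazard ratio per unit of predictor (one within-arm SD) runs from about 1.02 to 1.15 for an upward shift. For a downward shift of 0.8 it is 0.93 (25%/35%) or 0.87 (20%/40%). With an arm term it is about 1.00.

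**Topography.** Section 7.2.1 gives the device to 100 participants, about 50 per arm at 1:1. At n = 100 the rate without arm is about 4–13% over the same range.

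**If arm entered only as one more screened candidate**, it would pass p < 0.10 with probability Φ(β√120/2 − 1.645). That is 0.29 at 27.5%/32.5%, 0.71 at 25%/35% and 0.998 at 20%/40%.

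**The case against.** The best defence is that the plan is silent on arm, not opposed to it. The candidate predictors form an open list, and arm would almost certainly survive the screen where the bias is largest. That stands as a limit on the size: the worst figures apply only if arm is never offered as a candidate. Nothing requires it to be offered, though, and at 25%/35% screening would still drop it in about 29% of trials.

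The documents also suggest that compensation may be modest. Section 2.2 reports only small degrees of it in the tapering studies, and Section 12 calls it minimal in prior work. With a small shift, or equal drop-out, little or nothing goes wrong.

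A reader might infer more than the documents support:

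- **That the analysis stops at a one-variable Cox model.** It does not. A multivariable model follows, but it does not name arm either.
- **That control participants cannot compensate.** Everyone moves from their own brand to research cigarettes in Baseline Phase 2. The accurate statement is that controls have no nicotine cut after randomisation.
- **That Aim 2 claims compensation causes drop-out.** The plan says associated with.
- **That all of Aim 2 is compromised.** Predictors fixed before randomisation are balanced by arm in expectation.
- **That the n = 400 error rates apply to puff measures.** These come from 100 people.

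**Conclusion.** The concern holds in a bounded form. Section 9.2 neither requires arm in the Aim 2 Cox models nor fixes the timing of the compensation measures. A post-randomisation CO or puffing predictor can therefore carry the arm effect.

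The bias needs both drop-out and the predictor to differ by arm. Without a drop-out difference it is nil. At 25%/35% it is small to moderate, and at 20%/40% it can be large. These splits and the 0.25–0.8 SD shifts are my assumptions. The case for a change does not rest on the upper figures: even without inflation, a hazard ratio pooled over arms does not isolate the response to reduced nicotine. The correction is cheap, so it should be made.

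**What to change.** In Section 9.2:

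1. Force arm into both Cox steps as a covariate, exempt from the p < 0.10 screen. For categorical predictors, add a Cox model with arm alongside the Kaplan-Meier curves. Use a covariate instead of a stratum so that arm's own hazard ratio for drop-out is reported. Take that hazard ratio from a model without post-randomisation CO, because otherwise it is conditional on compensation.
2. Define compensation as change in CO from the last pre-randomisation value (Visit 3, Day 21), entered as a time-updated covariate. Start time at risk at Visit 4 (Day 42), the first CO after randomisation. Without this start, anyone leaving earlier would have no compensation value, or a zero by construction. Report drop-outs before Day 42 separately.
3. Pre-specify a compensation-by-arm term, kept whatever its p-value, and report the hazard ratio within the reduced-nicotine arm.
4. Keep baseline dependence and metabolism phenotype as fixed predictors.
5. Treat topography as descriptive. At 30% drop-out the reduced-nicotine arm gives about 50 × 0.30 = 15 events, and the device is not reissued after Visit 8.

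**Cost.** Wording and modest programming. CO is already taken at every clinic visit and the sample size is unchanged.

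The late start loses early drop-outs from the CO estimate. At constant hazard, 1 − 0.70^(3/18) = 5.8% of 400, or about 23 of 120. In the reduced-nicotine arm at 30% drop-out, 60 events become about 48. The 95% interval per SD is then the estimate multiplied and divided by exp(1.96/√48) = 1.33, against exp(1.96/√120) = 1.20 for all 120 events. With 15 topography events the factor is exp(1.96/√15) = 1.66.
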